Furthermore, since the approval of the first anti-TNF agent for the treatment of CD in 1998, the availability of newer biological agents, including anti-integrin (vedolizumab), Janus kinase (JAK) inhibitors (tofacitinib), and anti-IL12/23 (ustekinumab) has improved the care of moderate to severe UC. However, none of these subsequently approved therapies have demonstrated significant improvement in effect size relative to anti-TNF. Moreover, among those patients who do respond, up to 45% will lose response over time ([Roda 2016](#)). Current therapies used in the

treatment of UC apply a one-size-fits-all approach without regard to genetic or biologic variations in the patient. Existing approaches continue to leave unmet patient need.

Given established clinical validation of the target with PF-06480605, the current placebo-controlled Phase 2 induction study is designed to demonstrate the efficacy of PRA023 in subjects with moderately to severely active UC. In addition, this induction study is designed to assess the effectiveness of the genetic CDx for the purpose of selection of subjects whose disease is driven by the TL1A pathway and therefore, have a higher response rate to treatment with an anti-TL1A antibody. The study is also designed with an open-label extension study to ensure that subjects who benefit from the therapy have the option to continue therapy.

In parallel to this study, an open-label CD study (PRA200-103) will be conducted to demonstrate the proof of concept of PRA023 for induction therapy in subjects with moderately to severely active CD.

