### 2.2 Secondary Objectives

All objectives below refer to comparison of PRA023-treated subjects vs placebo-treated subjects in Cohort 1. For the objectives where the CDx status is a variable, a comparison of subjects in both Cohort 1 and Cohort 2 will be conducted.

- To compare the efficacy of PRA023 vs placebo for induction of endoscopic improvement at Week 12
- To compare the efficacy of PRA023 vs placebo for induction of clinical response at Week 12
- To compare the efficacy of PRA023 vs placebo in CDx+ subjects (Cohort 1 + Cohort 2) for induction of clinical remission at Week 12
- To compare the efficacy of PRA023 vs placebo for induction of symptomatic remission at Week 12
- To compare the efficacy of PRA023 vs placebo for induction of histologic remission at Week 12
- To compare the efficacy of PRA023 vs placebo for induction of histologic-endoscopic mucosal improvement at Week 12
- To compare the efficacy of PRA023 vs placebo in CDx+ subjects (Cohort 1 + Cohort 2) for induction of endoscopic improvement at Week 12
- To compare the efficacy of PRA023 vs placebo in CDx+ subjects (Cohort 1 + Cohort 2) for induction of clinical response at Week 12
- To compare the efficacy of PRA023 vs placebo in CDx+ subjects (Cohort 1 + Cohort 2) for induction of symptomatic remission at Week 12
- To compare the efficacy of PRA023 vs placebo in CDx+ subjects (Cohort 1 + Cohort 2) for induction of histologic remission at Week 12
- To compare the efficacy of PRA023 vs placebo in CDx+ subjects (Cohort 1 + Cohort 2) for induction of histologic-endoscopic mucosal improvement at Week 12
- To compare the efficacy of PRA023 in CDx+ (Cohort 1 + Cohort 2) vs CDx negative (CDx-) subjects for induction of clinical remission at Week 12

- To compare the efficacy of PRA023 vs placebo for induction of mucosal healing at Week 12
- To compare the efficacy of PRA023 vs placebo in CDx+ subjects (Cohort 1 + Cohort 2) for induction of mucosal healing at Week 12
- To compare the efficacy of PRA023 vs placebo for change in Inflammatory Bowel Disease Questionnaire (IBDQ) at Week 12
- To compare the efficacy of PRA023 vs placebo in CDx+ subjects (Cohort 1 + Cohort 2) for change in IBDQ at Week 12
- To compare the efficacy of PRA023 vs placebo in CDx+ subjects per alternative algorithm (Cohort 1 + Cohort 2) for induction of clinical remission at Week 12

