  - The proportion of subjects with histologic-endoscopic mucosal improvement (defined as Geboes score  $\leq 3.1$  **and** endoscopy subscore  $\leq 1$  with no friability), in CDx+ subjects (Cohort 1 + Cohort 2) treated with PRA023 compared to CDx+ placebo-treated subjects at Week 12.
  - The proportion of subjects with clinical remission (defined as endoscopic subscore of 0 or 1, rectal bleeding subscore of 0, and stool frequency subscore of 0 or 1 and not greater than Baseline) in CDx+ subjects (Cohort 1 + Cohort 2) treated with PRA023 compared to in CDx- subjects treated with PRA023 at Week 12.
  - The proportion of subjects with mucosal healing (defined as Geboes score  $\leq 2B.1$  **and** endoscopy subscore of  $\leq 1$ ) at Week 12.
  - The proportion of subjects with mucosal healing (defined as Geboes score  $\leq 2B.1$  **and** endoscopy subscore of  $\leq 1$ ), in CDx+ subjects (Cohort 1 + Cohort 2) treated with PRA023 compared to CDx+ placebo-treated subjects at Week 12.
  - The proportion of subjects with IBDQ response, as defined by  $\geq 16$ -point increase from Baseline at Week 12.
  - The proportion of subjects with IBDQ response, as defined by  $\geq 16$ -point increase from Baseline, in CDx+ subjects (Cohort 1 + Cohort 2) treated with PRA023 compared to CDx+ placebo-treated subjects at Week 12.
  - The proportion of subjects in the 3-component Modified Mayo Score clinical remission (as defined by endoscopic subscore of 0 or 1, rectal bleeding subscore of 0, and stool frequency subscore of 0 or 1 and not greater than Baseline), in CDx+ subjects per alternative algorithm (Cohort 1 + Cohort 2) treated with PRA023 compared to CDx+ placebo-treated subjects per alternative algorithm at Week 12. The 3-component Modified Mayo Score ranges from 0-9 and includes rectal bleeding, stool frequency, and endoscopic assessment domains.

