## 4 INVESTIGATIONAL PLAN

### 4.1 Study Design

This is a multi-center, double-blind, randomized, placebo-controlled proof of concept study designed to assess the safety, tolerability, and efficacy of PRA023 following 12 weeks of induction therapy in subjects with UC. This study will be conducted under the aegis of a DMC and will commence following the demonstration of an acceptable safety profile of PRA023 at a dose of  $\geq 500$  mg in multiple ascending dose study in normal healthy volunteers (Study PR200-101).

The study has 4 periods (Screening Period, Induction Period [IP], Open-Label Extension [OLE] Period, and Follow-Up [FU] Period). The study will have 2 Cohorts that will enroll subjects in a sequential fashion utilizing an adaptive design as described below.

**Cohort 1:** Following the Screening Period, approximately 120 eligible subjects with moderately to severely active UC will enter the IP and be randomized in a 1:1 fashion to receive IV administration of PRA023 1000 mg on Week 0/Day 1, followed by 500 mg on Weeks 2, 6, and 10, or placebo at the same timepoints. Randomization will be stratified by CDx status of positive (CDx+) or negative (CDx-) and prior biologic experience (yes/no) at Week 0/Day 1. Subjects who discontinue from the study drug will have a follow-up period of 12 weeks after last dose.

**Cohort 2:** Enrollment will continue into Cohort 2 when any stratification limit of Cohort 1 enrollment is completed. When approximately 80% of subjects in Cohort 1 (i.e., ~96 subjects) have reached Week 12 or early terminated from the study, the DMC will conduct an unblinded analysis of clinical efficacy in CDx+ subjects and will recommend whether to continue enrollment into Cohort 2. The sample size for CDx+ subjects (combining Cohort 1 and Cohort 2) will be approximately 40, in the case where Cohort 2 completes enrollment as planned. For Cohort 2, eligible subjects who are CDx+ will enter the IP and be randomized in a 1:1 fashion to receive IV administration of PRA023 1000 mg on Week 0/Day 1, followed by 500 mg on Weeks 2, 6, and 10, or placebo at the same timepoints. Randomization will be stratified by prior biologic experience (yes/no) at Baseline. Subjects who discontinue from the study drug will have a follow-up period of 12 weeks after last dose.

Subjects who complete the 12-week IP from either Cohort will have the option to enter OLE. During OLE, starting at Week 14 visit:

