### 8.2 Justification of Sample Size

The study is planned to randomize up to approximately 170 subjects, approximately 120 in Cohort 1 and up to 50 in Cohort 2. A sample size of 60 per arm in Cohort 1 will enable a statistical power of > 80% for the primary endpoint at 1-sided significance level of 0.025 using Cochran-Mantel-Haenszel (CMH), assuming clinical remission rate of 5% for placebo and 24% for PRA023. Additionally, the sample size will confer > 80% power to achieve statistical significance for the 1st secondary endpoint of endoscopic improvement with an overall 1-sided alpha level of 0.025, assuming the endoscopic improvement rates are 15% and 38% for placebo and PRA023 groups, respectively.

Additionally, for analyses of the CDx+ population (combining CDx+ subjects from Cohort 1 and Cohort 2), a sample size of 40 per arm will provide a statistical power of  $\geq 80\%$  at a 1-sided alpha level of 0.025, according to a group sequential design with a non-binding futility interim analysis when approximately 18 subjects are anticipated per arm reach Week 12, assuming clinical remission rate of 5% for placebo and 31% for PRA023.

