### 9.3.2 Evaluation of Efficacy Parameters

The efficacy assessment will test for the difference between PRA023 and placebo groups in FAS.

The primary endpoint will be analyzed and compared between PRA023 and placebo treatment groups in FAS from Cohort 1. The primary endpoint, the proportion of subjects achieving clinical remission, will be tested between the 2 treatment groups at 1-sided significance level of 0.025 using CMH with stratification factors at randomization. If significant, the 1st secondary endpoint of proportion of subjects achieving endoscopic improvement will be tested between the 2 treatment groups at 1-sided significance level of 0.025. If significant, the 2nd, 3rd, 4th, and 5th secondary endpoints will be tested sequentially, each at 1-sided significance level of 0.025. Testing for statistical significance will stop when the first endpoint is not statistically significant at level of 0.025 and all remaining p values will be nominal.

Treatment difference for primary and secondary endpoints for Cohort 1 will be estimated along with 95% CI for all subjects in FAS. The secondary endpoints in CDx+ subjects will be summarized and compared between PRA023 and placebo groups in FAS for CDx+, while the treatment difference will be estimated with 95% CI. Additional efficacy analysis will be detailed in SAP.

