1 INTRODUCTION

This statistical analysis plan (SAP) addendum describes the additions or modifications to the approved SAP V01 dated 10 August 2022 and is based on the study protocol version 4.0.

The SAP addendum covers the following topics of statistical analyses of the Induction Period for Cohort 1 following the corresponding database lock:

- Modification of Section 6.10, for the approach to multiplicity adjustment.
- Addition of an interim analysis for subjects with CDx+ based on protocol specified algorithm and the alternative algorithms.

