3.1 DEFAULT CDx+

The protocol specified CDx status, called default UC algorithm, was used for stratification of the randomization in Cohort 1. As designed, CDx+ subjects will be enrolled in Cohort 2 following the completion of Cohort 1 enrollment. The analysis for CDx+ related secondary endpoints will be analyzed when all subjects in Cohort 2 complete Week 12 or early discontinue. The combined CDx+ subjects across Cohort 1 and Cohort 2 will constitute the CDx+ FAS for these secondary endpoints.

At the time of this SAP addendum, the planned interim analysis when approximately 80% of subjects in Cohort 1 (i.e., ~96 subjects) have reached Week 12 or early terminated from the study has been completed. DMC reviewed the unblinded interim efficacy and safety data for all available subjects and CDx+ subjects on 19 October 2022. Following the review, DMC recommended to continue the enrollment of Cohort 2, and informed a total sample size of 48 for the cohort.

Based on the emerging information related to CDx development and validation, the Sponsor has made the decision to conduct an additional analysis for CDx+ subpopulation based on Cohort 1 data to assess the effect size of PRA023 in CDx+ subjects. In addition to the subgroup analysis based on CDx status for the primary endpoint, [Table 2](#) lists endpoints that will be assessed for the Cohort 1 CDx+ subpopulation. The methods of analysis are similar to those specified in SAP V01, with the following exceptions:

- The analysis sets are defined as CDx+ subjects who are randomized and treated in Cohort 1.
- No statistical hypothesis testing will be performed between PRA023 and Placebo treatment groups, while 95% confidence intervals will be presented for the estimation of treatment difference.

Table 2 Analyses for CDx+ Population in Cohort 1

Endpoints	Treatment Difference
Proportion of subjects in 3-component Modified Mayo Score clinical remission at Week 12	Included in subgroup analysis of the primary endpoint
Proportion of subjects with endoscopic improvement, as defined by endoscopy subscore ≤ 1 with no friability) at Week 12	Risk difference and 95% CI
Proportion of subjects in 3-component Modified Mayo Score clinical response at Week 12	Risk difference and 95% CI
Mean change in Partial Mayo Score over time Mean change in PRO-2 Score over time	Difference of LS mean and 95% CI
Fold change in hsCRP over time Fold change in fecal calprotectin over time	Ratio of geometric means and 95% CI

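### The only CDx+ versus CDx- endpoint compares PRA023-treated subjects alone, so it mixes prediction with prognosis; the supplied documents state no contrast of the two placebo-adjusted effects.

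*Protocol*

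**What the plan says.** Protocol 2.2 lists the objective "To compare the efficacy of PRA023 in CDx+ (Cohort 1 + Cohort 2) vs CDx negative (CDx-) subjects for induction of clinical remission" at Week 12. Protocol 3.2 turns it into the proportion in clinical remission "in CDx+ subjects (Cohort 1 + Cohort 2) treated with PRA023 compared to in CDx- subjects treated with PRA023 at Week 12". Every other CDx endpoint in 3.2 compares PRA023 with placebo among CDx+ subjects only.

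The purpose is given in Protocol 1.2: "this induction study is designed to assess the effectiveness of the genetic CDx for the purpose of selection of subjects". SAP addendum 3.2, on alternative algorithms, asks whether a CDx call changes the effect of PRA023 relative to placebo.

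Three other places bear on the point:

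- **Design.** Protocol 4.1 and 8.1 randomise Cohort 1 1:1 with CDx status as a stratification factor. Both CDx groups therefore have randomised placebo controls. Cohort 2 takes CDx+ subjects only.
- **Testing.** Protocol 9.3.2 takes the primary endpoint and the first five secondary endpoints in sequence; after the first failure, "all remaining p values will be nominal". The CDx+ versus CDx- endpoint is twelfth in the 3.2 list and does not appear in Table 1 of the SAP addendum.
- **Subgroups.** SAP addendum 3.1 opens its list of Cohort 1 CDx+ analyses with "In addition to the subgroup analysis based on CDx status for the primary endpoint". It states no difference between the two subgroup effects.

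**The concern.** CDx status is a genetic classification, not an assigned treatment. CDx+ and CDx- subjects may have different outcomes on placebo. Protocol 1.1 itself reports that TL1A polymorphisms are associated with disease severity. A comparison confined to the PRA023 arm cannot separate a marker that predicts benefit from the drug from one that predicts a better or worse course on any treatment. The error can run either way: it can create apparent prediction or hide real prediction.

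Pooling adds a second difficulty. All CDx- subjects come from Cohort 1, while the CDx+ group also includes Cohort 2, so the comparison is partly non-concurrent. Subtracting placebo within each CDx group removes shifts between cohorts that affect both arms alike; the PRA023-only comparison does not.

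At stake is how the trial is read on whether the CDx should select patients. The data for a direct answer will exist, but the named endpoint does not estimate it.

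**Working it through.** **1. The identity.** Let A+ and A- be PRA023 remission, and P+ and P- placebo remission, in CDx+ and CDx-. Then

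A+ − A- = [(A+ − P+) − (A- − P-)] + (P+ − P-).

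The first term is the difference in drug effect and the second is purely prognostic. The two sides of the question agree only when P+ = P-.

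**2. Inputs from Protocol 8.2.** Cohort 1: 60 per arm, 5% placebo and 24% PRA023. CDx+ pooled: 40 per arm, "assuming clinical remission rate of 5% for placebo and 31% for PRA023". No sample size or power is stated for CDx+ versus CDx-. The nearest stated figure is power of at least 80% for PRA023 versus placebo in CDx+. A pooled-variance two-proportion formula at 1-sided 0.025 gives 87.1% (Fisher exact 84.7%), ignoring the futility look, so that figure is reproduced.

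**3. CDx+ share of Cohort 1 (not stated; two derivations).**

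- From the interim: about 18 CDx+ per arm among 96/2 = 48 per arm, assuming all 18 are in Cohort 1. 18/48 = 37.5%, giving 22.5 CDx+ and 37.5 CDx- per arm.
- From the Cohort 2 total of 48 in SAP addendum 3.1: 24 per arm, so 40 − 24 = 16 CDx+ per arm in Cohort 1. 16/60 = 26.7%, leaving 44 CDx- per arm.

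**4. Contrast implied by the plan's rates.** The CDx- PRA023 rate is (0.24 − share × 0.31)/(1 − share): 19.8% at the 37.5% share and 21.5% at 26.7%. With 5% placebo in both groups, the difference in effects is 31 − 19.8 = 11.2 points or 31 − 21.5 = 9.5 points. Here the PRA023-only difference has the same value, so the error is zero.

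**5. Size of the error when placebo rates differ (hypothetical; no test is assigned to this endpoint).** Set the drug effect to 19 points in both groups, so true prediction is nil. Hold overall placebo remission at 5% and enumerate exactly an unstratified 1-sided 0.025 CMH test on PRA023-treated subjects, 40 CDx+ versus 38 (or 44) CDx-.

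| Prognostic difference | Placebo CDx+ / CDx-, 37.5% share | Favours CDx+ | Placebo CDx+ / CDx-, 26.7% share | Favours CDx+ |
|---|---|---|---|---|
| 0 points | 5.0% / 5.0% | 2.4% | 5.0% / 5.0% | 2.6% |
| 5 points | 8.1% / 3.1% | 7.1% | 8.7% / 3.7% | 7.8% |
| 10 points | 11.3% / 1.3% | 16.8% | 12.3% / 2.3% | 18.1% |

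With overall placebo fixed at 5%, the largest possible difference is 0.05/0.375 = 13.3 points at the first share and 0.05/0.267 = 18.8 points at the second.

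**6. The opposite direction.** Keep CDx+ at 31% versus 5% and CDx- PRA023 at 19.8%, but let CDx- placebo be 10%. The true contrast is 26.0 − 9.8 = 16.2 points, while the PRA023-only difference stays at 11.2.

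**7. Precision of the missing contrast.** SE² = [A+(1−A+) + P+(1−P+)]/n+ + [A-(1−A-) + P-(1−P-)]/n-, at the rates in step 4; half-width = 1.96 × SE. Power is for the contrast in step 4 at 1-sided 0.025.

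| Data | SE (37.5% / 26.7% share) | 95% half-width, points | Power |
|---|---|---|---|
| Cohort 1 | 0.131 / 0.146 | 25.6 / 28.6 | 13.5% / 9.6% |
| Cohort 1 + 2 | 0.109 / 0.107 | 21.4 / 21.0 | 17.5% / 14.3% |

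The pooled PRA023-only comparison has a half-width of 19.1 or 18.8 points, so it is only a little more precise.

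**The case against.** The strongest reply is that the gap may not exist. The SAP supplied is an addendum that "describes the additions or modifications to the approved SAP V01 dated 10 August 2022", and Protocol 9.3.2 leaves further efficacy analyses to the SAP. SAP V01 may hold an interaction estimate. This stands, and it limits the conclusion to the documents supplied.

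Second, the ingredients appear to be planned: a subgroup analysis of the primary endpoint by CDx status in Cohort 1, and PRA023 versus placebo in pooled CDx+ subjects. This also stands. But two subgroup effects reported side by side do not give their difference or its interval. SAP addendum 3.2 plots each CDx+ effect against the overall Cohort 1 effect, which contains those same CDx+ subjects.

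Third, the sentence in Protocol 1.2 goes on to describe the selected subjects as having a higher response rate on treatment, which a PRA023-only comparison does describe. That is a fair reading of the endpoint as description. It does not make the endpoint a measure of added benefit over placebo.

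Fourth, the error is zero at the plan's rates, the 10-point case is extreme, and the endpoint carries no confirmatory weight. All true. The illustrations show sensitivity, not an expected error.

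Finally, the added contrast has low power and would rarely settle the matter. That is a reason to present it as an estimate with its interval, not a reason to rely on a slightly narrower interval for a different quantity.

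**Conclusion.** The concern holds. The named CDx+ versus CDx- endpoint measures prediction only under equal placebo remission, and neither the protocol nor the SAP addendum states the contrast that would remove that assumption. The error equals the difference in placebo remission between the groups, whatever its sign. The identity is exact on the risk-difference scale. The rejection rates rest on assumed placebo differences, a common 19-point effect and an inferred CDx+ share.

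The primary analysis, testing hierarchy, sample size and interim decision rule are unaffected. This is an inexpensive improvement the sponsor should make, with medium confidence because SAP V01 was not available.

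**What to change.** Keep the endpoint and add to the SAP:

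> The difference in treatment effect by CDx status for clinical remission at Week 12, (PRA023 minus placebo in CDx+) minus (PRA023 minus placebo in CDx-), will be estimated on the risk-difference scale with a 95% CI, in Cohort 1 and in Cohort 1 + Cohort 2. This is estimation only.

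The Cohort 1 estimate is concurrent and stratified by CDx. In addition:

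- label the PRA023-only comparison as descriptive and report placebo remission by CDx status beside it;
- state that the contrast was added after the DMC review of October 2022;
- if SAP V01 already has the contrast, refer to it in Protocol 3.2 instead;
- optionally, show the positive-minus-negative contrast for each alternative algorithm next to the plot in SAP addendum 3.2.

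The cost is wording and one extra estimate, with no new data and no alpha. The drawback is the low precision shown in the working, so the result should not be presented as a confirmatory test.

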### 6.1 Study Visit Procedures

A written, signed informed consent form (ICF) must be obtained from each subject prior to performing any study procedure. Medical/surgical history, medication record (prior and concomitant medications and therapy), and a physical examination including vitals will be obtained for all subjects at the Screening Visit. A series of laboratory and diagnostic/clinical tests and evaluations will be performed. At least two visits to the clinical facility may be necessary to complete all screening procedures, including an endoscopy. The endoscopy should be performed after all other eligibility criteria have been met and within 28-5 days of randomization to allow 3-component Modified Mayo score calculation.

Subjects may be re-screened one time at the discretion of the Sponsor if they fail their initial screening.

For Cohort 2 - the first screening test after informed consent has been obtained should be buccal swab for CDx status identification, unless already known from study PR100-105 (global sample collection study). If the buccal swab testing shows a result of CDx+, the subject may complete all other screening procedures as per [Table 1](#). If the buccal swab is CDx- the subject will be screen failed. The 35-day screening window additional study assessments need not begin until the first study assessment post ICF and CDx status is obtained.

After randomization, all subjects will be evaluated frequently through a series of physical examinations, and laboratory tests and assessments for safety and efficacy as described in the Schedule of Study Assessments tables ([Section 6.1.1](#)).

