### 8.1 Randomization

Subjects will be randomized in a 1:1 ratio based on two stratification factors: CDx status (+/-) and prior biologic experience (yes/no) in Cohort 1. If the study is expanded in Cohort 2, only CDx+ subjects will be randomized in a 1:1 ratio based on prior biologic experience (yes/no). Eligible subjects will be assigned a subject randomization number at baseline by the IRT system upon confirmation of study eligibility. Subjects who are re-randomized in OLE will retain their original subject numbers.

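### Does admitting only default CDx+ subjects to Cohort 2 distort the pooled remission endpoint for the alternative CDx algorithm?

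*Protocol*

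**What the plan says.** Protocol section 3.2 closes its list of secondary endpoints with clinical remission at Week 12 "in CDx+ subjects per alternative algorithm (Cohort 1 + Cohort 2) treated with PRA023 compared to CDx+ placebo-treated subjects per alternative algorithm". Section 2.2 has the matching objective.

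Entry to Cohort 2 is restricted. Section 8.1 states: "If the study is expanded in Cohort 2, only CDx+ subjects will be randomized in a 1:1 ratio". Section 6.1 adds for that cohort: "If the buccal swab is CDx- the subject will be screen failed". Neither sentence says which algorithm makes the call. SAP addendum section 3.1 supplies the link: "The protocol specified CDx status, called default UC algorithm, was used for stratification of the randomization in Cohort 1". It describes Cohort 2 enrolment under the same heading. That Cohort 2 was selected on the default call is therefore an inference, but no section names another entry algorithm.

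On analysis, protocol section 9.3.2 says "The secondary endpoints in CDx+ subjects will be summarized and compared between PRA023 and placebo groups in FAS for CDx"+, with a 95% confidence interval, and leaves further efficacy analyses to the SAP. The addendum modifies SAP V01 and deals with the Cohort 1 analysis. Its section 3.2 examines five alternative algorithms in Cohort 1 and plots each remission difference against the overall Cohort 1 effect. Its Table 1 hierarchy does not contain the pooled alternative-algorithm endpoint.

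**The concern.** The default CDx+ endpoints pool the two cohorts without difficulty, because Cohort 2 was selected on the same call that defines their population. The alternative-algorithm endpoint is different. Its population is defined by one call, while the second cohort was selected on another.

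The pooled set therefore holds a larger share of double-positive subjects than Cohort 1 does. If default-positive subjects respond better, as the sample-size assumptions suppose, an alternative algorithm with no predictive value could show a larger pooled effect than the overall Cohort 1 effect. More subjects recruited under the same rule would not remove this, and a reader could not see it without the cross-classification of the two calls. At stake is a fair reading of which algorithm picks out responders.

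**Working it through.** **Inputs**

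- All subjects, protocol section 8.2: "assuming clinical remission rate of 5% for placebo and 24% for PRA023", a difference of 19 points.
- Default CDx+, same section: "approximately 18 subjects are anticipated per arm reach Week 12, assuming clinical remission rate of 5% for placebo and 31% for PRA023", a difference of 26 points.
- Cohort 1 of about 120 (section 8.2). Cohort 2 of 48 (addendum section 3.1: "DMC recommended to continue the enrollment of Cohort 2, and informed a total sample size of 48 for the cohort").
- Default-positive share of Cohort 1, p. It is not stated and is derived three ways. The interim figures give 36/96 = 37.5%. A target of 80 CDx+ in total gives (80 − 48)/120 = 26.7%, or (80 − 50)/120 = 25% with the planned maximum of 50 in Cohort 2.
- Alternative-positive share among default-positives (a) and default-negatives (b). The documents give neither, so both are assumptions and are varied.

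**The plan's own figures first.** Power = Φ{[Δ√n − 1.96√(2p̄(1−p̄))] / √(p₁(1−p₁)+p₂(1−p₂))}.

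- 60 per arm, 5% vs 24%: (1.4717 − 0.9760)/0.4795 = 1.034, power 84.9%. The protocol says above 80%.
- 40 per arm, 5% vs 31%: (1.6444 − 1.0649)/0.5113 = 1.133, power 87.2% before any loss from the futility look. The protocol says at least 80%.

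Both reproduce.

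**Size of the shift.** Assume that only default status modifies the effect and that 24% is the all-comer rate in Cohort 1.

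- Default-negative effect d₋ = (19 − 26p)/(1 − p): 16.7, 16.5 and 14.8 points at p = 25%, 26.7% and 37.5%.
- Default-positive share among alternative-positives in Cohort 1: w₁ = pa/[pa + (1−p)b].
- The same share when pooled: w = (120pa + 48a)/[120pa + 48a + 120(1−p)b].
- Shift = (w − w₁)(26 − d₋).

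If the two calls are unrelated (a = b), the pooled effect is (120×19 + 48×26)/168 = 21.0 against 19.0 in Cohort 1. The shift is 2.0 points whatever p is.

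| a / b | Shift at p = 25% | p = 26.7% | p = 37.5% |
|---|---|---|---|
| 95% / 5% | 0.74 | 0.68 | 0.45 |
| 80% / 20% | 1.9 | 1.8 | 1.4 |
| 40% / 40% | 2.0 | 2.0 | 2.0 |
| any / 0% | 0 | 0 | 0 |

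Over all a and b the maximum is about 2.2 points at p = 25% and 2.0 at p = 37.5%. If 24% is read as the default-negative rate itself, the maximum is 1.3 to 1.7 (with 50 in Cohort 2).

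**Against sampling error.** At 40%/40% and p = 37.5% the pooled set has 18 + 30 + 19.2 = 67.2 subjects, or 33.6 per arm, with remission of 5% vs 26%. SE = √[(0.05×0.95 + 0.26×0.74)/33.6] = 8.45 points, so the shift is 2.0/8.45 = 0.24 SE. At 95%/95% there are 79.8 per arm, SE is 5.48 and the ratio 0.365. In the limit a = b = 100% (84 per arm, SE 5.34) it is 0.374.

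**Would standardising to the Cohort 1 mix help?** Estimate the difference by default status and combine it with weight w₁. Total error is RMSE = √(SE² + shift²), with the Cohort 1 mix taken as the target.

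| Case | Crude SE | Crude RMSE | Standardised SE = RMSE |
|---|---|---|---|
| 40/40, p = 26.7% | 8.45 | 8.68 | 8.81 |
| 80/20, p = 26.7% | 7.88 | 8.09 | 8.33 |
| 30/10, p = 25% | 12.44 | 12.62 | 13.29 |
| 40/40, p = 37.5% | 8.45 | 8.68 | 8.57 |
| 95/95, p = 25% | 5.48 | 5.84 | 5.74 |

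Standardising loses in the first three cases and gains about 0.1 point in the last two. The default-negative stratum, 120(1−p)b, is 3.75 to 4.5 subjects at 95%/5% and 7.5 to 9 at 30%/10%, both arms together.

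**The case for a change.** The strongest case for a change is that the mechanism is real, its direction is known on the protocol's own rates, and both conditions for it are plausible. The sponsor built the CDx because it expects default-positive subjects to respond better, and an alternative algorithm that agreed with the default on everyone would have no purpose. Nothing in the documents reviewed weights, splits or restricts the endpoint, and a remedy would cost one sentence and a few table rows.

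The mechanism and the arithmetic stand. Four things weaken the conclusion.

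- The shift is measured against the Cohort 1 mix, which the protocol never makes the target. The named population is the two cohorts together, and the pooled estimate describes it. The Cohort 1 mix may also be shaped by that cohort's enrolment limits.
- The misreading is not planned. The only comparison with the overall effect, in addendum section 3.2, sets Cohort 1 estimates against the Cohort 1 effect, and those are free of the shift.
- The proposed estimate would sit beside the crude one and would be less accurate in most cases.
- The addendum covers Cohort 1, so its silence on a later pooled analysis is expected. SAP V01 may deal with it.

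**Conclusion.** No change is needed. The pooled endpoint does over-represent double-positive subjects relative to Cohort 1, by a mechanism worth at most about 2.2 points, or 0.37 SE, on the plan's rates, and nothing if either condition fails.

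The comparison remains randomised 1:1 within each cohort. Error rates and the test hierarchy are untouched, and estimates without the shift are already planned for each listed algorithm. Standardising trades a small shift for a larger variance and usually loses. An analyst may usefully show the pooled result by default CDx status and note that Cohort 2 informs only double-positive subjects, but that is ordinary presentation.

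The conclusion rests on these assumptions: Cohort 2 entry used the default call (inferred from addendum section 3.1), only default status modifies the effect, 24% is the all-comer rate, and p lies between 25% and 37.5%. The bound belongs to those rates. With 50 in Cohort 2 and no effect at all in default-negatives, a case outside the plan, the maximum would be about 5 to 6 points.
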